### **Baseline Measure Information**

Table 1. Baseline characteristics of both groups

	Placebo (n= 14 patients)	Levothyroxine (n=18 patients)	P value
Sex (n=% female)	71.42%	55.55%	NA
Age (years)	63.85 DE+/- 15	69.22 DE+/- 8.7	0.41
Diabetes Mellitus (yes or no)	11 (78.57%)	13 (72.22%)	1.00
Hypertension (yes or no)	12 (85.71%)	16 (88.88%)	1.00
Weight (Kg)	67.90 +/- 13.83	67.01 +/- 11.32	0.88
Obesity (BMI >30 kg/m  )	1 (7.14%)	3 (6.6%)	0.61
ERC G3a (45-59 ml/min/1.73m  )	0	3 (6.6%)	0.23
ERC G3b (30-44 ml/min/1.73m  )	2 (14.28%)	4 (22.22%)	0.67
ERC G4 (15-29 ml/min/1.73m  )	5 (35.71%)	7 (38.88%)	1.00
ERC G5 ( <15 ml/min/1.73m  )	7 (50%)	4 (22.22%)	0.14
eGFR (ml/min/1.73m  )	9.96 +/- 18.3	13.35 +/- 28	0.16
TSH (uim/L)	4.46 +/- 1.68	5.93 +/- 2.2	0.02 ®
Protein urine 24/hours (gr/24hrs)	1.28 +/- 1.28	1.71 +/- 1.20	0.14
Cr.s (mg/dl)	3.65 +/- 1.65	2.46 +/- 1.13	0.05 ®
Albumine (mg/dl)	3.99 +/- 0.41	3.8 +/- 0.41	0.24
Tryglicerides (mg/dl)	194 +/- 75.3	144.66 +/- 91.76	0.09
Cholesterol (mg/dl)	170.57 +/- 45.96	165.5 +/- 59.67	0.67
LDL (mg/dl)	75.5 +/- 19	102.38 +/- 31.42	0.01 ®
Hemoglobin (gr/dl)	11.37 +/- 1.21	11.95 +/- 1.61	0.17
BP systolic (mmHg)	148.14 +/- 27.7	160 +/- 19.4	0.17

BP diastolic (mmHg)	79 +/- 11.72	81.83 +/- 8.2	0.60
IECA o ARA-2 (n=%)	100	100	1.00
Allopurinol (n=%)	100	100	1.00
Statines (n=%)	100	100	1.00

- Study-Specific Measure
- Age:
  - Age, Continuous:
  - Age, Categorical:
    - >18 and <80 year
  - Age, Customized: Customizable age categories
- Sex/Gender
  - Sex: Female, Male
- Race and Ethnicity
  - Race and Ethnicity Not Collected (Hispanic race)
- Region of Enrollment: Guadalajara, Mexico
  - **Measure Type:** Mean

**Measure of Dispersion** Standard Deviation

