### **Statistical Test of Hypothesis and Method**

In the case of quantitative variables, the data are shown as average or median with standard deviation, according to the distribution, be it parametric or non-parametric, respectively.

The nominal variables are shown with frequencies or percentages.

For intergroup and continuous variable comparisons, in the case of qualitative variables, chi2 and, in the case of quantitative variables, the Student's T test or Mann-Whitney U test depending on the distribution of the sample.

The statistical analysis will be carried out with the statistical program SPSS, version 20.

In all cases a value of  $p < 0.05$  will be accepted as significant.

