### **Method of Estimation (or Statistical Test of Hypothesis or Other Statistical Analysis required)**

- Mean Difference (Final Values)
  - Risk Ratio (RR) (Adverse effects)

**Parameter Dispersion Type :** Standard Deviation

Adverse Event Information

All-Cause Mortality: no death

Eventos adversos graves: no serious adverse event

Other (Not Including Serious) Adverse Events:

During the study the following adverse effects were presented: Urinary tract infection in a single patient of the placebo group (7.14%) and nervousness in two patients of the levothyroxine group (11.11%) (RR 1.55 95% CI (0.15-15.47), value p = 1.0).

None left the study because of the adverse effect. Adverse events were not severe according to the severity scale

Table of non-serious adverse events		
arm Levothyroxine	(N=1) 7.14%	Infections and Infestations (Urinary tract infection)
Arm placebo	(N=2) 11.11%	Psychiatric Disorder (Anxiety)

Duration of urinary tract infection: five days, without complications.

Anxiety duration time: three days, without complications.

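### The adverse-event table gives the events to the opposite arms from the sentence above it; its two arm labels are most likely exchanged

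*Combined protocol and SAP*

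**What the plan says.** Everything at issue stands in one place, the Adverse Event Information under Method of Estimation.

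- The sentence: "Urinary tract infection in a single patient of the placebo group (7.14%) and nervousness in two patients of the levothyroxine group (11.11" per cent).
- The comparison attached to it: "RR 1.55 95% CI (0.15-15.47), value p = 1.0". The direction of the ratio is not given. The list of estimation methods says only "Risk Ratio (RR) (Adverse effects").
- The table of non-serious events, first row: "arm Levothyroxine (N=1) 7.14% Infections and Infestations (Urinary tract infection").
- The table, second row: "Arm placebo (N=2) 11.11% Psychiatric Disorder (Anxiety").
- The line on duration uses the table's term, not the sentence's: "Anxiety duration time: three days, without complications".

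The arm sizes come from elsewhere in the document. Table 1 under Baseline Measure Information has the column heading "Placebo (n= 14 patients") and gives 18 for levothyroxine. Number of Units Analyzed repeats 18 and 14, and Number of Baseline Participants gives 19 and 19. For categorical comparisons the Statistical Test of Hypothesis and Method section specifies "in the case of qualitative variables, chi2", without saying whether a continuity correction applies.

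**The concern.** The sentence and the table cannot both be right: each event is credited to one arm in the text and to the other in the table. The counts, percentages and event types travel together in both places, and only the arm differs.

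Tolerability and safety of levothyroxine is one of the objectives in the Detailed Description, and this is the only adverse-event table. Read alone, it shows no anxiety events on the study drug and two on placebo. A reader who extracts only the table, for example for a registry entry or a pooled safety summary, would record the comparison in the wrong direction if the sentence is the correct version. With three events in total, the whole non-serious safety record depends on those two labels.

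**Working it through.** **Inputs.** Counts of 1 and 2, percentages of 7.14 and 11.11, and the risk ratio with its interval and p value, all from Adverse Event Information. Analysed arms: levothyroxine 18, placebo 14. Baseline arms: 19 and 19.

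**1. Percentages on the analysed arms.**

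| Version | Levothyroxine | Placebo |
|---|---|---|
| Sentence | 2/18 = 11.11% | 1/14 = 7.14% |
| Table labels, recomputed | 1/18 = 5.56% | 2/14 = 14.29% |
| Table as printed | 7.14% | 11.11% |

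The table's own percentages carry the other arm's denominator. They fit only if the labels are exchanged.

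**2. Reproducing the stated risk ratio from the sentence.** RR = (a/n1)/(b/n2), with log-scale standard error SE = √(1/a − 1/n1 + 1/b − 1/n2).

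- RR = (2/18)/(1/14) = 1.556.
- SE = √(1/2 − 1/18 + 1/1 − 1/14) = √1.373 = 1.172.
- 95% limits: 1.556 × exp(±1.96 × 1.172) = 0.156 to 15.46.
- p = 1.0 by Fisher's exact test and by continuity-corrected chi-squared; 0.70 by uncorrected chi-squared.

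The document states 1.55 (0.15 to 15.47), p = 1.0. The agreement is close but not exact. Truncation explains 1.55 and 0.15. The upper limit differs by 0.01.

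**3. The same calculation from the table's labels.**

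- Levothyroxine against placebo: (1/18)/(2/14) = 0.389. The SE has the same terms, so it is again 1.172, and the limits are 0.039 to 3.87.
- Inverted, placebo against levothyroxine: (2/14)/(1/18) = 2.571, limits 0.259 to 25.56.
- p = 0.57 (Fisher), 0.82 (corrected chi-squared), 0.40 (uncorrected chi-squared).

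None of these matches the stated result in either direction.

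**4. What the printed percentages alone can show.** 11.11/7.14 = 1.556 and 7.14/11.11 = 0.643. Because the direction is not stated, a ratio of 1.56 could be read off the printed percentages under either labelling. The discrimination comes from placing the counts over the arm sizes, as in steps 1 to 3.

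**5. Could the baseline denominators rescue the table?** With 19 per arm the percentages are 1/19 = 5.26% and 2/19 = 10.53%, and the ratio of the larger to the smaller is 2.00. These match neither the printed percentages nor the printed ratio, whichever arm the events are placed in.

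**The case against.** The best case on the other side is about weight. This is probably a labelling slip in a results table, not a defect of design or analysis. The version that agrees with the arm sizes and the risk ratio stands directly above the table, so an attentive reader can resolve the conflict. The primary outcome and the listed secondary outcomes are untouched. The events are non-serious, and the comparison is non-significant under both labellings by every test tried. Nothing was miscalculated in substance either: the percentages and the ratio are right for the sentence. All of this stands, and it limits the importance of the point. It does not remove the contradiction, because a table is often read without its text.

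The smaller requests can also be challenged. A complaint of nervousness may properly be coded as anxiety, though the document does not say that this happened. The stated p = 1.0 is compatible with the planned chi-squared test if a continuity correction was used. That the ratio pools all events and compares levothyroxine with placebo can be inferred from the sentence. These objections are fair: the term, the caption and the name of the test are tidying, and the evidence on the arm labels does not depend on them.

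Finally, the stated ratio is reproduced only to within rounding or truncation. That is true, but the gap is trivial beside the alternatives of 0.39 and 2.57.

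**Conclusion.** The concern holds. The sentence and the table contradict each other on the arm for all three reported events. Both printed percentages and the stated risk ratio agree with placebo 1/14 and levothyroxine 2/18, and no other allocation checked reproduces them. The table's two arm labels are therefore most likely exchanged.

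The conclusion assumes that the percentages and the ratio were computed per analysed patient (18 and 14), which the exact match of both percentages supports. It establishes internal consistency only. The document cannot show which version agrees with the source records.

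The point should be fixed, but its reach is limited. It reverses the apparent direction of the safety comparison for anyone relying on the table alone and changes no efficacy result.

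**What to change.** Check the arm and the event term of the three events against the adverse-event forms, then correct whichever version is wrong.

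- **If the forms agree with the sentence, as expected:** exchange the two arm labels, so that the table shows placebo 1/14 (7.14%) with urinary tract infection and levothyroxine 2/18 (11.11%) with nervousness or anxiety. The risk ratio stays as it is.
- **If the forms agree with the table:** correct the sentence, change the percentages to 5.56% (levothyroxine) and 14.29% (placebo), and replace the risk ratio with 0.39 (0.04 to 3.87) and its matching p value.

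In either case, use one term for nervousness/anxiety in the sentence, the table and the duration line. Caption the ratio as any adverse event, levothyroxine versus placebo, and name the test behind the p value.

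The cost is a source check of three events and, in the expected case, two row labels, one term, one caption and the name of one test. No new data or analysis is needed in that case.

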### Exclusion Criteria:

- Chronic dialysis (peritoneal dialysis or hemodialysis)
  - Primary hypothyroidism or preexisting thyroid disease
  - Use of levothyroxine.
  - TSH> 10uiml / L and TSH <2.5 0uiml / L
  - Positive thyroid antibodies
  - Ischemic heart disease in less than 6 months
  - Cardiac arrhythmia
  - Use Medications (Levothyroxine synthesis, see Table 2)
  - Anxiety disorder
  - Pregnancy

- Do not accept consent
- Patients weighing <50 kg and > 80kg

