**Number of Baseline Participants**

38 patients ( 19 arm Levothyroxine and 19 arm placebo)

**Number of Units Analyzed** 32 patients ( 18 arm Levothyroxine and 14 arm placebo)

**Analysis Population Type** Participants

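### The only between-arm safety estimate (RR 1.55, p = 1.0) is an unlabelled any-adverse-event ratio, printed straight after the nervousness count as if it were the nervousness result

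*Combined protocol and SAP*

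**What the plan says.** Under Method of Estimation, the document declares the safety measure as "Risk Ratio (RR) (Adverse effects"), that is, adverse effects as a class with no event type named. The Adverse Event Information text that follows gives two events. The first is "Urinary tract infection in a single patient of the placebo group (7.14"%). The second, with the ratio directly behind it, is "nervousness in two patients of the levothyroxine group (11.11%) (RR 1.55 95% CI (0.15-15.47), value p = 1.0").

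The table beneath that text has one row per arm. The levothyroxine row shows one urinary tract infection (7.14%) and the placebo row shows two patients with anxiety (11.11%). This is the reverse of the narrative.

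The analysed population is "32 patients ( 18 arm Levothyroxine and 14 arm placebo"), and the number at baseline is "38 patients ( 19 arm Levothyroxine and 19 arm placebo"). The Detailed Description lists tolerability and safety of levothyroxine among the objectives. The Exclusion Criteria include "Anxiety disorder", without a reason. No other between-arm safety estimate appears.

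**The concern.** The ratio names no outcome and sits immediately after the nervousness count, so the natural reading is that 1.55 with p = 1.0 is the comparison for nervousness. It is not. One infection on placebo supplies the whole denominator risk. On the narrative's account, nervousness occurred in two patients on levothyroxine and in none on placebo, and no single number in the document shows that contrast.

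Safety is a stated objective and this is its only comparative result. A reader could take p = 1.0 as evidence that nervousness does not differ between arms. The opposite arm assignment in the table adds to the problem, because the direction of every safety contrast depends on which of the two accounts is right.

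**Working it through.** **Inputs.** From the narrative: 2 patients with nervousness on levothyroxine and 1 with urinary infection on placebo. From the analysed population: 18 and 14 patients. I take nervousness (narrative) and anxiety (table) to be the same event.

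**1. Reproduce the printed figure.**
- RR = (2/18)/(1/14) = 0.1111/0.0714 = 1.556.
- SE(log RR) = √(1/2 − 1/18 + 1/1 − 1/14) = √1.373 = 1.172.
- 95% CI = exp(0.442 ± 1.96 × 1.172) = 0.156 to 15.46.
- Fisher exact p = 1.0. Chi-square gives 1.0 with Yates correction and 0.70 without.

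This matches "RR 1.55 95% CI (0.15-15.47), value p = 1.0" to within rounding or truncation. The printed ratio therefore pools the two event types. The three patients are all the adverse events reported, so the same number is the risk ratio for any reported non-serious adverse event. As a risk difference it is 11.1 − 7.1 = +4.0 points (Newcombe 95% CI -21.6 to +26.4).

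**2. Separate the events, following the narrative.** Intervals for the differences are Newcombe 95% CIs built from the Wilson limits of each arm.

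| Event | Levothyroxine | Placebo | Difference, points (95% CI) | Fisher p | RR with 0.5 added per cell (95% CI) |
|---|---|---|---|---|---|
| Nervousness | 2/18 (11.1%) | 0/14 (0%) | +11.1 (-11.9 to +32.8) | 0.49 | 3.9 (0.20 to 76) |
| Urinary infection | 0/18 (0%) | 1/14 (7.1%) | -7.1 (-31.5 to +11.4) | 0.44 | 0.26 (0.01 to 6.0) |

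Worked for nervousness:
- The Wilson limits are 3.1% to 32.8% for 2/18 and 0% to 21.5% for 0/14.
- Lower limit = 11.1 − √((11.1 − 3.1)² + 21.5²) = -11.9.
- Upper limit = 11.1 + √((32.8 − 11.1)² + 0²) = +32.8.
- Fisher p = P(both cases on levothyroxine) + P(both on placebo) = 153/496 + 91/496 = 0.308 + 0.183 = 0.49.

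The raw ratio is not estimable for nervousness because no placebo patient had it. The corrected 3.9 is (2.5/19)/(0.5/15) and depends on the added halves.

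**3. Test the arm labels.** The percentages are 1/14 = 7.14% and 2/18 = 11.11%, which fit the narrative's arms. With the table's arms they would be 1/18 = 5.56% and 2/14 = 14.29%. If the table's arms were nevertheless correct:
- Any event: (1/18)/(2/14) = 0.39 (0.04 to 3.87), Fisher p = 0.57.
- Nervousness: 0/18 against 2/14, difference -14.3 points (-39.9 to +6.1), Fisher p = 0.18.

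**4. Vary the denominators.** With 19 per arm, assuming no events in the six patients not analysed, the any-event ratio is (2/19)/(1/19) = 2.0 (0.20 to 20.2). Nervousness is then 2/19 against 0/19, Fisher p = 0.49.

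**The case against.** The strongest defence is that the pooled ratio is what the method line declares. It gives a risk ratio for adverse effects as a class, and any-event incidence is a conventional, well-defined quantity. The sentence also lists both events before giving the ratio, and the document draws no safety conclusion from p = 1.0. This stands. A reader might infer that 1.55 estimates no risk at all; the documents do not support that. The fault is the missing label, the placement, and the absence of any comparison by event.

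A second defence is that two cases carry almost no information. This also stands. A reader might see a safety signal being masked, but nervousness alone gives p = 0.49 and its interval includes no difference, so the most that can be claimed is an imbalance. The printed interval of 0.15 to 15.47 already shows how little is known, and the pooled difference does not exclude a sizeable excess either. Few events are, however, a reason to show counts by event and not only an unlabelled ratio.

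Third, the exclusion of anxiety disorder comes with no stated rationale, so it does not establish that nervousness was a pre-specified event of interest. Singling it out is post hoc. The request for per-event reporting therefore covers both events alike.

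Finally, the table already has a row per event with n and a percentage. It lacks the zero cells, however, and its arms contradict the narrative, so it cannot stand in for the missing comparison.

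**Conclusion.** The point holds as one of labelling and reporting. Separating the events moves the nervousness contrast from the pooled +4.0 points to +11.1 points and puts urinary infection on the other side of zero. It does not change the conclusion that the data are uninformative: no comparison reaches p < 0.05.

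The per-event figures rest on the narrative's arm assignment and on 18 and 14 patients. The percentages make the narrative the likelier account, but it would be wrong to treat 2/18 against 0/14 as settled while the table says otherwise. Under the table's labels the imbalance reverses. The matter bears on a stated objective but not on the primary outcome.

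**What to change.** In the Adverse Event Information text and table:

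1. Reconcile the narrative and the table against source data before any figure is reissued, and correct whichever is wrong.
2. Report n/N by arm for each event term, including zero cells, with a risk difference and 95% CI (Newcombe or exact). Use one term for nervousness/anxiety throughout and state the denominator.
3. If RR 1.55 is kept, label it as patients with any non-serious adverse event, name the test behind the p value, and separate it from the nervousness clause.
4. State that the data are too few to exclude a sizeable excess of nervousness; on the narrative's arms the upper limit is 32.8 points.

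The cost is a source check on three patients and a few lines of re-analysis on data already in hand. If the narrative's arms are confirmed, the safety statement becomes slightly less favourable.

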### **Adverse Event Reporting Description**

with follow-up every 4 weeks, with thyroid profile control tests and adverse effects will be reported and follow-up. It will be valued in accordance with intensity According to the criteria CTC v. 3.0 (1-5), start date and end thereof, as well as the treatment received.

### **Overall Limitations and Caveats**

Overall Limitations and Caveats At least 12 to 25 patients are needed in each arm.

There were missed follow-ups in both arms but more in the placebo arm.

#### ▼ Locations: Mexico

Kidney health clinic, Civil Hospital of Guadalajara

Guadalajara, Jalisco, Mexico, 44280

Contact: [name] [name] [[contact]](mailto:[contact])

Contact: [name] [name] [[contact]](mailto:[contact])

Principal Investigator: [name]

**Table 2** Drugs that interact with levothyroxine

- Drugs that interact with the synthesis of thyroid hormones and / or Levothyroxine: Amiodarone, Lithium and Heparin

Interactions with medications that reduce the absorption of levothyroxine:

- Anti-acids (proton pump inhibitors) can inhibit absorption. People should take levothyroxine four to six hours before or after taking these antacids.
- Iron supplements: can inhibit absorption. People should take levothyroxine four to six hours before or after taking these
- Sucralfate: can inhibit absorption. People should take levothyroxine eight hours before or after taking these
- Ciprofloxacin: can inhibit absorption. People should take levothyroxine four to six hours before or after taking these.
- Raloxifene: can reduce the absorption of levothyroxine, although evidence to date is not sufficient to establish the scope of the interaction. In one case, the separation of the two drugs in 12 hours appeared to avoid interaction.
- Glucocorticoids
- Chloroquine
- Sevelamer
- Orlistat
- tyrosine kinase inhibitors

Drugs that potentiate the effect of levothyroxine

- Salicylates (medicines used to relieve pain and reduce fever),
- dicumarol (medicine to prevent blood clotting),
- furosemide in high doses of 250 mg (diuretic medicine),
- Clofibrate (medicine to reduce the level of fats in the blood).

Effect of levothyroxine on other medications

- Decreases the effect of oral hypoglycemic agents up to 5%
- Increases warfarin effect
